# 7.3.2 Exclusion Criteria

Individuals who meet any of the following exclusion criteria will not be eligible to participate in the study:

- 1. *If enrolled in a prior UX003 clinical study*, the subject experienced a safety-related event in a prior UX003 clinical study that, in the opinion of the Investigator and sponsor, precludes resuming UX003 treatment.
- 2. Undergone a successful bone marrow or stem cell transplant or has any degree of detectable chimaerism with donor cells.

- 3. Presence or history of any hypersensitivity to rhGUS or its excipients that, in the judgment of the Investigator, places the subject at increased risk for adverse effects.
- 4. Pregnant or breastfeeding at Baseline or planning to become pregnant (self or partner) at any time during the study.
- 5. Use of any investigational product (drug or device or combination) other than UX003 within 30 days prior to Baseline, or requirement for any investigational agent prior to completion of all scheduled study assessments.
- 6. Presence of a condition of such severity and acuity that, in the opinion of the Investigator, warrants immediate surgical intervention or other treatment or may not allow safe study participation.
- 7. Concurrent disease or condition, or laboratory abnormality that, in the view of the Investigator, places the subject at high risk of poor treatment compliance or of not completing the study, or would interfere with study participation or introduce additional safety concerns.

# 7.3.3 Removal of Subjects from Therapy or Assessment

In accordance with the Declaration of Helsinki, subjects have the right to withdraw from the study at any time for any reason. The Investigator and Ultragenyx also have the right to remove subjects from the study. Ultragenyx must be notified of all subject withdrawals as soon as possible. Ultragenyx also reserves the right to discontinue the study at any time for either clinical or administrative reasons and to discontinue participation of an individual subject or Investigator due to poor enrollment or noncompliance, as applicable. Female subjects who become pregnant will be withdrawn from study drug (refer to Section 7.5.2.6).

Subjects may be removed from the study for the following reasons:

- Occurrence of an unacceptable AE
- An illness that, in the judgment of the Investigator or Ultragenyx, might place the subject at risk or invalidate the study
- At the request of the subject, Investigator, or Ultragenyx, for administrative or other reasons
- Protocol deviation or unreliable behavior

If the reason for removal of a subject from the study is an AE, the AE and any related test or procedure results will be recorded in the source documents and transcribed onto the CRF. Each clinically significant abnormal laboratory value or other clinically meaningful abnormality should be followed until the abnormality resolves or until a decision is made that it is not likely to resolve. If such abnormalities do not return to normal within 30 days after

the last dose given, their etiology should be identified and Ultragenyx should be notified. All unscheduled tests must be reported to Ultragenyx immediately.

The termination visit should be completed by all subjects who do not complete the Week 144 end of study visit. The termination visit should be completed within 30 days of the last dose of study drug. Efficacy assessments performed within 30 days will not be repeated at the termination visit. If the termination visit occurs after Week 48, blood for serum biomarkers of inflammation will not be collected and BOT-2 assessments will not be conducted.

# 7.3.3.1 Stopping Rules

Individual subjects who experience any unexpected and possibly, probably, or definitely drug-related serious adverse events (SAEs; Section 8.5.3) that represent a change in the nature or an increase in frequency of the serious event from their prior medical history or known MPS 7-related medical issues will be assessed as to whether the subject will continue on the study.

The IRB/EC will be informed should unexpected and possibly, probably, or definitely study drug-related SAEs occur. A full evaluation of the event will be performed in order to make a decision regarding what actions to take, including whether to recommend stopping the study.

# 7.4 Treatments

Approximately 20 subjects may be dosed QOW for up to 144 weeks. All subjects will receive 4 mg/kg UX003 QOW unless data from prior studies define a different dose either for that subject or the use of UX003 in general.

# 7.4.1 Identity of Investigational Product

UX003 (recombinant human beta-glucuronidase, rhGUS) is a multimeric glycoprotein produced using a genetically engineered Chinese hamster ovary cell line to secrete the human lysosomal enzyme, beta-glucuronidase. The mature form of the enzyme consists of 651 amino acids. The drug product is formulated at 2 mg/mL rhGUS in UX003 formulation buffer. Refer to the Investigational Brochure or Pharmacy Manual for details about buffer excipients. UX003 is supplied as a sterile solution for IV administration packaged in single use 10 mL glass vials and is stored at 2 to 8°C.

The study drug is manufactured, packaged, and labeled according to Good Manufacturing Practice (GMP) regulations.

# 7.4.2 Study Drug Infusion Procedure

UX003 will be administered QOW by slow IV infusion over a period of approximately 4 hours. Subjects will be pre-medicated prior to infusions and study drug will be administered on a rate-schedule that minimizes the potential for IARs. The infusion will

begin at a low rate that will be gradually increased, as tolerated by the subject, until the planned maximum rate is reached.

Refer to the Study Reference Manual for additional details on study drug infusion procedures.

# 7.4.2.1 Pre-Dose Medication

Approximately 30 - 60 minutes prior to each infusion of study drug and after performing pre-infusion efficacy assessments, all subjects will be pretreated with an appropriate dose of antihistamine medication. Non-sedating antihistamines, such as cetirizine or loratadine, are preferred. For subjects who have a history of IARs or other risk factors (e.g. history of allergies), a sedating antihistamine (e.g. diphenhydramine or chlorpheniramine) may be administered. Antipyretic medications such as ibuprofen or acetaminophen may be administered at the discretion of the Investigator. For subjects with IARs, slowing the infusion rate is important but additional premedication with agents such as H2 blockers, or steroids may be considered.

# 7.4.2.2 Infusion Procedure

The amount of UX003 will be determined based on subject weight (in kg). The volume of study drug calculated to deliver the correct dose will be withdrawn from the vial and aseptically transferred to an infusion bag of normal saline. Undiluted UX003 must never be infused.

**PLEASE NOTE FOR PREPARATION OF INFUSION SOLUTIONS**: UX003 (rhGUS) is a recombinant protein and is therefore sensitive to bubbles and aggressive mixing that can lead to denaturation and loss of enzyme activity. When preparing diluted infusion solutions, the product should be withdrawn VERY SLOWLY through a sufficiently large needle (18 gauge) to minimize shear and turbulence. When adding study drug solution to an infusion bag, this must be done slowly, with liquid to liquid contact and without generating bubbles or turbulence; the bags should be rocked gently for mixing. Shaking of vials or infusion bags or "volutrols" devices in which aggressive mixing and bubbles can occur are not acceptable.

Study drug will be administered by slow IV infusion over approximately 4 hours. Infusions will be administered on a rate-schedule involving a slower infusion rate initially followed by an increase in rate that minimizes the potential for infusion reactions and may be slowed to manage or reduce IARs. Refer to the Pharmacy Manual for additional details on the infusion rate schedule. Topical eutectic mixture of local anesthetic (EMLA) cream or equivalent may be applied to the IV site prior to the infusion to ease the pain of placing an IV line.

At the discretion of the Investigator, an in-dwelling IV catheter (such as a Port-a-Cath® or other brand) may be inserted if there are difficulties in achieving IV access for the QOW infusions.

Equipment necessary for resuscitation must be available during study drug infusion.

# 7.4.3 Selection of Doses in the Study

The planned UX003 dose of 4 mg/kg is based on doses examined in an ongoing Phase 2 clinical study in MPS 7 subjects, and further supported by nonclinical studies in the MPS 7 mouse model and relevant species. The nonclinical data support chronic QOW administration of UX003 at dose levels up to 4 mg/kg, with a relative 5-fold safety factor. The pharmacologic studies in the MPS 7 mouse showed that both 2 mg/kg and 4 mg/kg were effective doses with only a few tissues or cell types such as osteocytes responding better at 4 mg/kg versus 2 mg/kg. Safety was the same at all doses.

The Phase 1/2 study (UX003-CL201) in MPS 7 subjects evaluated UX003 administered at doses of 1, 2, and 4 mg/kg QOW. Preliminary results suggest the percent reduction in urinary GAG excretion is greatest with the 4 mg/kg dose with mean reductions of approximately 60% observed, while the reductions at 2 mg/kg were in the 40-50% range. Additionally, during the forced dose titration process, the reductions in uGAG observed at 4 mg/kg lessened when subjects returned to the 2 mg/kg dose, suggesting a decrease in efficacy. These changes in uGAG exceeded an absolute difference of 10% and were of sufficient magnitude to consider the 4 mg/kg dose a more appropriate dose. In the clinical studies of ERT for other MPS disorders, changes in uGAG were able to differentiate between effective and less effective dose regimens, with reductions of >50% associated with substantial efficacy based on clinical measures. Infusions at 4 mg/kg in 3 subjects in the UX003-CL201 study for 8 weeks showed no safety issues, and there have been no drug-related IARs at any dose to date. Therefore, the 4 mg/kg dose appears to be well tolerated at this time.

The therapeutic ERT doses in prior successful programs for other MPS disorders (0.58, 0.5 and 1 mg/kg weekly for MPS 1, 2, 4A, and 6, respectively) were based on comparable doses that exhibited efficacy in their respective animal models. PK data in MPS 1, MPS 2, MPS 4A, and MPS 6 subjects demonstrate that doses of 0.2 to 2 mg/kg are adequate to achieve enzyme concentrations of ~10-27 nM in the circulation. These enzyme levels are approximately 10- to 30-fold the uptake constants (1-2.7 nM) for the mannose 6 phosphate receptor and are believed to saturate delivery of enzyme to the tissues (Kakkis et al. 1994), (Kakkis et al. 1996a), (Kakkis et al. 2001), (Dvorak-Ewell et al. 2010). Similar uptake constants (1.2-2.6 nM) were obtained in studies with human MPS 7 fibroblast cells in vitro (Ultragenyx data). Studies with rhGUS in MPS 7 mice at doses of 4 mg/kg show that serum GUS concentrations of >10-fold the uptake constant were readily achieved and demonstrated that enzyme was delivered to a variety of important tissues, implying that the efficacious dose should be within this range (Grubb et al. 2008).

A higher dose is needed to provide the same rhGUS molar concentration as other MPS enzymes, since rhGUS enzyme has two active sites per tetramer and the molecular weight (332 kDa tetramer) is approximately 4-fold higher compared to the other MPS enzymes. The equivalent number of moles of enzyme active sites would require about two

times the efficacious dose for other MPS enzymes on a mass or milligram basis. Therefore, approximately 1-4 mg/kg UX003 is estimated to achieve the same molar concentration of active enzyme.

The QOW dosing regimen is supported by the long in vitro half-life and increased stability of rhGUS compared with other MPS enzymes. Data from the earliest MPS ERT studies showed that when human enzymes for MPS 1 or 2 were applied to deficient human fibroblasts, the half-life of the enzyme in the lysosome was on the order of 2-5 days (Kakkis et al. 1994), (Elaprase 2006) leading to weekly dosing frequency as the optimal choice. For rhGUS, this experiment showed a half-life of about 40 days, which is a substantial increase over MPS 1 or MPS 2 enzymes, which are dosed weekly. The rhGUS enzyme is also a more stable enzyme than the other MPS enzymes at neutral pH, as it might be exposed to the circulation before uptake by lysosomes. Both the increased half-life and stability of rhGUS indicate QOW dosing should be adequate in humans.

All subjects may receive up to 144 weeks of UX003 treatment. The treatment duration is sufficient to assess long-term safety and provide sufficient insight on sustained clinical effects and improvements in pediatric, adolescent, and adult efficacy of UX003 treatment in MPS 7 subjects.

# 7.4.4 **Prior and Concomitant Therapy**

# 7.4.4.1 Prohibited Medications

Subjects may not be enrolled if they have used any investigational product (other than UX003) or investigational medical device within 30 days prior to Baseline, or if they require any investigational agent prior to completion of all scheduled study assessments.

The use of genistein is specifically prohibited during study participation.

# 7.4.4.2 Permitted Medications

Subjects may receive concomitant medications as required.

For subjects enrolling from an Ultragenyx-sponsored clinical trial, medications (investigational, prescription, over-the-counter, and herbal) and nutritional supplements reported as ongoing at the primary study's End of Treatment visit and any new medications taken prior to Baseline will be reviewed and recorded at the Baseline visit. Any enrolling subject who had an early termination in the primary study will have their baseline concomitant medications collected in the same manner as a subject who is treatment naïve or enrolling from a non-Ultragenyx sponsored study (see following paragraph).

For subjects who are treatment naïve or who are enrolling from a non-Ultragenyx sponsored clinical trial, medications (investigational, prescription, over-the-counter, and herbal) and

nutritional supplements taken during the 30 days prior to Baseline will be reviewed and recorded.

At each visit, any concomitant medications added or discontinued during the study should be recorded on the CRF. The site personnel should record the following in the CRF: date and time the medication was taken, the dose and name of the medication, and the reason the medication was taken.

Medications administered prior to each infusion of study drug and any non-study therapies provided by the Investigator during study participation will be similarly recorded in the CRF.

# 7.4.5 Treatment Compliance

UX003 is not to be dispensed to subjects. UX003 will be administered by IV infusion by a qualified health care professional at the clinical site. The date, time, and volume of each dose of study drug administered to each subject must be recorded in the dispensing log for the study, as well as on the appropriate CRF.

#### 7.5 Study Procedures and Assessments

#### 7.5.1 Schedule of Events

Informed consent must be obtained prior to any study procedures. Subjects will be enrolled only after inclusion/exclusion criteria have been confirmed.

For subjects previously enrolled in the Ultragenyx-sponsored MPS 7 Phase 3 clinical study UX003-CL301, the Baseline Visit will be conducted in conjunction with the UX003-CL301 Week 48 study visit to avoid treatment disruption. Data collected at the UX003-CL301 Week 48 visit may serve as the Baseline data for this study. All additional Baseline assessments (not included in the UX003-CL301 Week 48 assessments), other than UX003 treatment, must also be completed prior to determination of eligibility. Following confirmation of eligibility, subjects will receive their first study drug infusion in this study and will return for assessments according to the Schedule of Events (Table 2.1).

For subjects enrolling from other Ultragenyx sponsored clinical studies, clinical outcome assessments including efficacy, echocardiogram (ECHO) and clinical laboratory tests performed during the final, or End of Treatment, visit from the primary (or feeder) study may be used as baseline assessments for this study if performed within 30 days of the Baseline visit as specified below.

*Subjects enrolling from an Ultragenyx sponsored clinical study* who had an early termination in their primary (or feeder) study will have their baseline assessments collected in the same manner as a subject who is treatment naïve or enrolling from a non-Ultragenyx sponsored study (see following paragraph).

For subjects who are treatment naïve or who are enrolling from a non-Ultragenyx sponsored clinical study, initial baseline safety and efficacy assessments will be performed within 30 days of the Baseline visit. All assessments scheduled on the same day as UX003 treatment must be performed prior to the first study drug infusion for this treatment and extension study.

For all subjects, Baseline study visits should be conducted at a primary site from an Ultragenyx sponsored clinical study. Following the Baseline visit, subjects may return to their primary, or Baseline, study site for all safety assessments, efficacy assessments, and infusions every 24 weeks through the end of study. Alternatively, the 24-week visits may be performed at the subject's local site if feasible. All other clinic visits, including assessments and infusions, may be performed at the subject's local site as appropriate.

Subjects will return to the clinic at 2-week intervals ( $\pm$  3 days) for study drug infusion and basic safety measures. Subjects will have assessment of uGAG levels and physical exams at 12-week intervals. Major assessment visits are scheduled at 24-week intervals ( $\pm$  7 days) through the end of study.

The end of trial is defined as the last visit of the last subject undergoing evaluation in the study. As the planned duration of treatment in this study is up to 144 weeks, the end of trial is defined as the Week 144 visit of the last subject. In the event the study is terminated by the Sponsor prior to Week 144, all subjects should complete a termination visit and the date of the last termination visit of the last subject would define the end of the trial. The termination visit should be completed within 30 days of the last dose of study drug. Efficacy assessments performed within 30 days will not be repeated at the termination visit. If the termination visit occurs after Week 48, blood for serum biomarkers of inflammation will not be collected and BOT-2 assessments will not be conducted.

The parameters to be assessed in Study UX003-CL202, along with timing of assessments, are provided in the Schedule of Events (Table 2.1). All assessments scheduled on the same day as a UX003 treatment day must be completed prior to the infusion on that day. Where caregiver assessments are required, the same individual should complete the assessment for consistency of reporting, when possible. Refer to the Study Reference Manual for additional details on specific assessments.

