- w. The MPS HAQ or HAQ/CHAQ should be performed for *UX003 treatment-naïve subjects and subjects enrolling from the MPS 7 Phase 3 Ultragenyx sponsored study UX003-CL301*. The MPS HAQ will be administered to all age groups. The CHAQ should be performed for pediatric subjects only (<14 years old). The HAQ should be performed for subjects ≥14 years old. Subjects will consistently complete the same questionnaire (HAQ or CHAQ) administered at baseline for the duration of the study regardless of whether their age changes from 13 to 14 during the study. The age-appropriate version of the PedsQL multidimensional fatigue module will be administered throughout the study. *For subjects enrolling from previous clinical trial with UX003*, these subject-reported outcome measures will only be administered if they were previously performed in their primary (or feeder) study.
- x. As part of the subject/parent/caregiver clinical global impression assessment, subjects/parents/caregivers will be asked to provide narratives of how treatment has impacted the subject's ability to complete activities of daily living.
- y. Liver and spleen size will be assessed qualitatively by physical examination.
- z. The termination visit should be completed by all subjects who do not complete the Week 144 end of study visit. The termination visit should be completed within 30 days of the last dose of study drug. Efficacy assessments performed within 30 days will not be repeated at the termination visit. AEs ongoing at 30 days following the last dose of study drug should have a comment in the source document by the Investigator that the event has recovered, recovered with sequelae, or stabilized. If the termination visit occurs after Week 48, blood for serum biomarkers of inflammation will not be collected and BOT-2 assessments will not be conducted.

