#### 7.5.2.10 Adverse Events

For subjects enrolling from an Ultragenyx-sponsored clinical trial, all AEs will be recorded from the time the subject signs the informed consent for this extension study and completion of the End of Treatment visit in the primary study until 30 days after the last dose of study drug. Adverse events reported as ongoing at the primary study's End of Treatment visit and any new AEs prior to Baseline will be reviewed and recorded at Baseline visit. Any enrolling subject who had an early termination in the primary study will have their baseline AE information collected in the same manner as a subject who is treatment naïve or enrolling from a non-Ultragenyx sponsored study (see following paragraph).

For subjects who are treatment naïve or who are enrolling from a non-Ultragenyx sponsored clinical trial, all AEs will be recorded from the time the subject signs the informed consent until 30 days after the last dose of study drug.

The determination, evaluation, reporting, and follow-up of AEs will be performed as outlined in Section 8.5. At each visit subjects will be asked about any new or ongoing AEs since the previous visit. Assessments of AEs will occur at each study visit.

Clinically significant changes from study baseline in physical examination findings, vital signs, and clinical laboratory parameters, will be recorded as AEs or SAEs, if appropriate.

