#### 8.5.4 Adverse Event Reporting to Ultragenyx

#### 8.5.4.1 General

All AEs (i.e. any new or worsening in severity or frequency of a pre-existing condition) with an onset after the subject signs consent for study participation must be promptly documented on the AE eCRF via the EDC system. The Principal Investigator is responsible for evaluating all AEs, obtaining supporting documents, and ensuring documentation of the event is adequate. Details of the AE must include severity, relationship to study drug, duration, and outcome.

For subjects enrolling from an Ultragenyx-sponsored clinical trial, all AEs will be recorded from the time the subject signs the informed consent for this extension study and completion of the End of treatment visit in the primary study until 30 days after the last dose of study drug. Adverse events reported as ongoing at primary study's End of treatment visit and any new AEs prior to Baseline will be reviewed and recorded at Baseline visit. Any enrolling subject who had an early termination in the primary study will have their baseline AE information collected in the same manner as a subject who is treatment naïve or enrolling from a non-Ultragenyx sponsored study (see following paragraph).

For subjects who are treatment naïve or who are enrolling from a non-Ultragenyx sponsored clinical trial, all AEs will be recorded from the time the subject signs the informed consent until 30 days after the last dose of study drug.

In addition, the Investigator should report any AE that occurs after this time period that is believed to have a reasonable possibility of being associated with study drug.

AEs ongoing at 30 days following the last dose of study drug should have a comment in the source document by the Investigator that the event has recovered, recovered with sequelae, or stabilized.

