# 8.5.5 Serious Adverse Events, Serious Adverse Drug Reactions, and Requirements for Immediate Reporting

Any SAE that occurs from the time of signing the ICF through 30 days following the last dose of study drug, including a clinically significantly abnormal laboratory test result that is considered serious, must be reported within 24 hours of knowledge of the event to Ultragenyx or its designee. These requirements apply equally to all subjects, regardless of the study phase or the at-risk subject's treatment assignment or dosage. All initial SAE reports must be followed by detailed descriptions. These should include copies of hospital case records and other documents when requested. SAEs will be reported by completing and submitting SAE report forms to Ultragenyx or designee.
Protocol Number: UX003-CL202 Amendment 3: 28 JUL 2016

Follow-up SAE information must be submitted in a timely manner as additional information becomes available. All SAEs regardless of relationship to study drug must be followed to resolution or stabilization if improvement is not expected.

All deaths, regardless of causality, from the time of consent through 30 days after last dose of study drug must be reported as an SAE to Ultragenyx or its designee within 24 hours of knowledge.

The Investigator also must notify the IRB/EC of the occurrence of the SAE, in writing, as soon as is practicable and in accordance with local law. A copy of this notification must be provided to Ultragenyx or its designee.

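### The adverse event window runs to day 30 after the last dose, but no contact is scheduled to cover its final part, and the end of trial can precede its close

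*Protocol*

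**What the plan says.** **The window.** Protocol 7.5.2.10 states, for treatment-naïve subjects and those from non-sponsor studies, that "all AEs will be recorded from the time the subject signs the informed consent until 30 days after the last dose of study drug". Subjects from sponsor studies have the same end point, and 8.5.4.1 repeats both rules. Section 8.5.5 applies the same limit to serious events ("Any SAE that occurs from the time of signing the ICF through 30 days following the last dose of study drug") and to fatal ones: "All deaths, regardless of causality, from the time of consent through 30 days after last dose of study drug must be reported".

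**The day-30 duty.** Section 8.5.4.1, and footnote z of Table 2.1, add: "AEs ongoing at 30 days following the last dose of study drug should have a comment in the source document by the Investigator", giving the event's outcome.

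**How events are found.** Section 7.5.2.10 ties this to visits: "Assessments of AEs will occur at each study visit", and subjects are asked at each visit about new or ongoing events.

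**The last visit.** Table 2.1 ends at Week 144 apart from the termination column. Footnote z limits that column: "The termination visit should be completed by all subjects who do not complete the Week 144 end of study visit". The termination visit has a latest day, day 30 after the last dose, but no earliest day.

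**The end of trial.** Section 7.5.1, referring to the final participant: "As the planned duration of treatment in this study is up to 144 weeks, the end of trial is defined as the Week 144 visit". If the sponsor stops the study early, the last termination visit takes its place.

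**The concern.** Followed exactly, the plan asks about adverse events only at visits, yet its safety window outlasts the last visit. The final part of the window has a recording duty but no planned question to feed it.

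Long-term safety is the primary objective, and there are only about 20 subjects and no data monitoring committee. Three things could be missed or learned late:

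- delayed reactions to the final infusions (7.5.2.11 names an immune-complex type among the infusion reactions);
- deaths or SAEs after the last visit;
- pregnancies in the 30 days after dosing during which contraception is still required, since the last scheduled pregnancy test is at Week 144 or termination.

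The day-30 comment on ongoing events also has no scheduled contact to supply it. For the last subject, the trial is formally over before the window closes.

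**Working it through.** The documents give no gap length to reproduce, so this is date arithmetic.

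**Inputs**
- Safety window: 30 days after the last infusion (protocol 7.5.2.10, 8.5.4.1, 8.5.5).
- Infusions every 14 days, window ± 3 days (7.5.1).
- Week 144 is Day 1009 (SAP Table 7.3.1): 1 + 7 × 144 = 1009. Week 142 is therefore 1 + 7 × 142 = Day 995.
- Week 144 is a major visit, window ± 7 days (Table 2.1, footnotes c and e).

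**Is there an infusion at Week 144?** The documents do not say outright. Table 2.1 shows treatment every 2 weeks across Weeks 50–144 and lists weight for drug preparation at Week 144, which points to a dose. A treatment duration of up to 144 weeks, with the SAP 5.8 exposure rule (last minus first infusion plus 14 days), fits a last dose at Week 142: 994 + 14 = 1008 days = 144 weeks, 72 infusions. A Week 144 dose gives 1008 + 14 = 1022 days = 146 weeks, 73 infusions. Both cases are carried forward.

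**Completers.** Gap = 30 − (day of Week 144 visit − day of last infusion).
- Last infusion at Week 142: 30 − (1009 − 995) = 16 days.
- Last infusion at Week 144: 30 − 0 = 30 days. Footnote b places same-day assessments before the infusion, so the AE enquiry at that visit cannot cover the days after the dose.
- Week 142 case with visit windows: the interval runs from 14 − 7 − 3 = 4 to 14 + 7 + 3 = 24 days, so the gap is 6 to 26 days.
- Over both cases: 6 to 30 days.

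**Early leavers.** Seen on day t after the last dose (t up to 30), the gap is 30 − t days. It is zero only if the visit falls on day 30.

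**Scale.** As a share of a completer's dosing period plus 30 days, the nominal gap is 16 / (994 + 30) = 1.6% or 30 / (1008 + 30) = 2.9%. If all 20 subjects complete (an assumption), it totals 20 × 16 = 320 to 20 × 30 = 600 person-days. One missed SAE in a subject with no other is 1/20 = 5 percentage points of subject incidence, if it counts as treatment-emergent: SAP 8.8.1 sets no upper time limit, whereas protocol 7.6.6.1 refers to onset during treatment.

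**After the change.** With a contact at or after day 30 for everyone, the gap is 0. On the nominal schedule that contact falls 16 or 30 days after a completer's Week 144 visit.

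**The case against.** The strongest reply is that the duties do not stop at the last visit. AEs are still to be recorded to day 30. SAEs and deaths must be reported within 24 hours of knowledge, and SAEs followed to resolution or stabilization. Pregnancies are followed to outcome, and where an AE led to removal, significant abnormalities are followed up (7.3.3). The day-30 comment presupposes that the Investigator finds out. All this stands. A reader might infer that the last days go wholly unobserved, and the documents do not support that. They support only that no enquiry is scheduled.

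The Study Reference Manual, not available here, may describe a call. But 7.5.1 places the timing of assessments in Table 2.1, which has none.

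Four other stronger readings also fail:

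- **That only related events volunteered by families are covered in the gap.** The 8.5.4.1 clause on events with a reasonable possibility of association applies after day 30. Inside the window, all AEs count.
- **That residual enzyme shows a risk.** Section 7.4.3 says "For rhGUS, this experiment showed a half-life of about 40 days", but this is a result in cultured cells, used to support dosing frequency. It is not evidence of risk in patients after the last visit.
- **That the results will claim a 30-day window that was not observed.** No planned analysis reports such a window: AE output is subject incidence, and SAP exposure adds 14 days, not 30.
- **That the trial ends for each completer at Week 144.** Section 7.5.1 defines the end by the last subject. The conflict touches only subjects whose 30 days run past that date.

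**Conclusion.** The concern holds as a gap in scheduled ascertainment. The plan sets a 30-day post-dose safety window and a day-30 status duty, but names no contact that reaches the end of that window, unless an early leaver's termination visit happens to fall on day 30. For completers the gap is 16 or 30 days on the nominal schedule and 6 to 30 days with the visit windows; for early leavers it is 30 − t days. The missing contact concerns every completer and every early leaver seen before day 30. The end-of-trial conflict is narrower, as set out above.

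The gap is small against nearly three years of follow-up, and how many events would be missed cannot be estimated from the documents. The case for change rests on safety being the primary objective and on the remedy being cheap. The figures assume that the visit windows are kept and that no call is specified in a manual not seen here.

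**What to change.** 1. Add to Table 2.1 one safety contact for every subject, completers and early leavers alike, at or shortly after day 30 following the last dose. Telephone is enough. It records new AEs, SAEs, deaths, pregnancies and the status of ongoing AEs. For a subject moving to another UX003 study or programme, it can be recorded at the first visit there.
2. In 7.5.1, define the end of trial as the last such contact of the last subject.
3. Reconcile the passages on whether an infusion is given at Week 144 (the Table 2.1 treatment and weight rows, the stated treatment duration, and the SAP exposure rule), so that day 30 can be dated.

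The cost is protocol wording, about 20 calls, and an end of trial about 2 to 4 weeks later (16 to 30 days on the nominal schedule). No new procedure is needed.
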